## **SHARE-S Aim 3: Shared Healthcare Actions & Reflections Electronic systems in Survivorship**

Wake Forest Baptist Comprehensive Cancer Center (WFBCCC)  
WFBCCC # 99420

Baseline analyses will include descriptive statistics of quantitative data on implementation outcomes, service outcomes, patient health outcomes, and background characteristics (i.e., clinical, demographic). The distributions of continuous variables will be examined to determine the presence of outliers and whether transformations are necessary for analysis. The primary goal of the statistical analysis of these measures will be to estimate standard deviations (SD) for use in future studies.

Additional analyses will include fitting mixed ANCOVA models (adjustment for baseline) to model the trajectory of patient health outcomes by time and group accounting for the repeated measures on a subject. The purpose of all of these models will be to obtain estimates of the SD of change adjusted for covariates of interest and the within-person correlation of the repeated measures, not to perform formal hypothesis testing. We will consider the different recall time frame for the quality of life measures when interpreting the results. In exploratory models we will examine the impact of adherence to SHARE-S on changes in the measures, subgroup analysis by cancer type, and we will examine the role of patient autonomy and self-efficacy as potential mechanisms. The purpose of these analyses will be to estimate SD and within-person correlation by subgroup and with adjustment for mechanisms; no formal hypothesis testing will be done.

Interview transcripts will be coded independently by the QPRO shared resource staff at WFBH. Twenty-five percent of the transcripts will be coded by two separate coders to ensure consistency of code application. Unresolved discrepancies reconciled by a third person. Using thematic analysis, the coded text will be iteratively reviewed and interpreted. The qualitative and quantitative analyses will be evaluated in a mixed-methods framework for consistency and discrepancies to refine the protocol for future studies. In particular, we will analyze the feasibility, acceptability and appropriateness data using a mixed-methods since these measures have not been validated in a similar sample. For example, if the qualitative interviews indicate that a particular subgroup of patients (e.g., by cancer type) perceive greater benefit from SHARE-S, then we will perform exploratory subgroup analysis of the quantitative data.

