### **1.0 Summary**

Nationally, there is a recognized gap in *implementing* guideline-concordant cancer survivorship care planning (SCP). Initial SCP guideline implementation efforts focused on document/information delivery and demonstrated limited efficacy for improving patient health outcomes. The proposed SHARE-S Implementation Program builds upon successful SCP studies based on the Chronic Care Model and aims to enhance SCP implementation, leveraging technology. SHARE-S will enhance SCP with self-management coaching and text/coaching support for adherence to the SCP guidelines that require self-management. We will conduct a single-arm pragmatic pilot study of SHARE-S implemented in clinical care (n=40). We will test the study protocols, implementation program, and complete mixed-methods data collection to guide future study planning. The primary goal of this study is to assess how successfully SHARE-S can be implemented in a clinical setting that already consistently provides survivorship care planning documents to improve guideline concordant survivorship care. We will also collect data on the feasibility of assessing the impact of SHARE-S on service outcomes and patient outcomes. The primary goal of the future larger study will be to assess SHARE-S in multiple clinical settings to improve implementation of guideline concordant survivorship care and thus patient health outcomes. SHARE-S is a novel approach to supporting patient self-management that is integrated with clinical care and may generalize to improving care for other chronic illnesses such as cardiovascular disease.

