### **3.2 Secondary Objective**

- 3.2.1** To assess additional implementation outcomes that evaluate preliminary implementation success (i.e., further assessment of adoption, acceptability, appropriateness, further assessment of feasibility, and fidelity).
- 3.2.2** To describe service outcome variability to inform future studies. We will assess service outcomes relevant to CoC requirements by reporting annual estimates for: (1) the estimated number of patients impacted by SHARE-S; (2) the cancer sites impacted by SHARE-S; and the (3) resources/processes utilized to enhance each of the chosen services if barriers were encountered. We will also assess safety and perceived patient-centeredness of care.
- 3.2.3** To describe patient health outcome variability to inform future studies (i.e., social role, physical functioning, anxiety, depression, fatigue, sleep disturbance, pain, cancer-specific quality of life, health behaviors, patient autonomy, self-efficacy for managing cancer, engagement with the survivorship care plan document, and satisfaction with care).
- 3.2.4** To evaluate the Implementation Program we will assess key Stages of Implementation Completion (SIC) milestones and processes for this pilot study of the Implementation Stage, measured at the clinic level.
- 3.2.5** To qualitatively assess implementation barriers and facilitators using semi-structured interviews that will be audio-recorded.
- 3.2.6** To examine how study results vary by cancer type.

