## **SHARE-S Aim 3: Shared Healthcare Actions & Reflections Electronic systems in Survivorship**

Wake Forest Baptist Comprehensive Cancer Center (WFBCCC)  
WFBCCC # 99420

the study name from the project list and enter the potential participant's email address and/or cell phone number as preferred by the patient (for this study we will use cell phone number only). By providing their email address or cell phone number, the patients verbally agree to be sent the study invitation messages and contacted for recruitment. After the referral has been executed, the eRefer portal provides study staff with the participant's contact information, allowing the study team to contact the participant.

The study team will then communicate with eligible patients either in person or remotely (e.g., telephone, myWakeHealth, mail) regarding their interest in study participation. The study coordinator will provide study information and answer questions to determine willingness to participate. After making sure the patient clearly understands the study procedures and agrees to follow them, the consent will be signed remotely or in person. If signed remotely, patients will be asked to send the form back to us by a secure means (e.g., REDCap, mail). In the case that the patient is consented remotely, either a hard copy or email attachment of the informed consent document will be provided to the participant. We will compensate participants up to \$100 based on level of assessment completion (\$25 for each assessment, \$25 for the interview). Study compensation will not be mentioned by the "Referrer".

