#### **Overview of Study-Related Activities**

	Pre-Study a	Baseline	SHARE-S b	Follow-up c
E-referral	X			
Informed consent	X			
Demographic/ Clinical Factors		X		
Self-Reported Measures		X		X
Intervention Adherence			X	
Acceptability Ratings				X
Semi-structured Interview				X
Adverse event evaluation			X	X

a Pre-study requirements listed in table must be completed within 60 days prior to registration.

b SHARE-S = study intervention, must be completed within one-year of registration.

c Follow-up visit to be completed the same day or within 30 days of the final intervention session.

[figure not shown]

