## **6.0 Outcome Measures**

## **SHARE-S Aim 3: Shared Healthcare Actions & Reflections Electronic systems in Survivorship**

Wake Forest Baptist Comprehensive Cancer Center (WFBCCC)  
WFBCCC # 99420

We will collect patient-reported data either remotely or in person at baseline (before the first coaching call) and follow-up (after the last coaching call).

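### The baseline-adjusted mixed model cannot supply the within-person correlation it is partly run to obtain, and 'group' is undefined in a single-arm study

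*Combined protocol and SAP*

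**What the plan says.** Section 7.2 (Data Analyses) plans "fitting mixed ANCOVA models (adjustment for baseline) to model the trajectory of patient health outcomes by time and group", allowing for repeated measures on the same person. It says these models are meant to provide "estimates of the SD of change adjusted for covariates of interest and the within-person correlation of the repeated measures", and it disclaims formal testing. Exploratory models follow, covering adherence, cancer type and possible mechanisms. Of these it says: "The purpose of these analyses will be to estimate SD and within-person correlation by subgroup and with adjustment for mechanisms". No covariance structure is given, and the text does not say whether the baseline value is also a response.

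Sections 1.0 and 3.0 describe a single-arm pilot; the accrual goal is 40. Section 6.0 places the patient-reported measures "at baseline (before the first coaching call) and follow-up (after the last coaching call". The table in section 5.2 has one follow-up column, with the note "Follow-up visit to be completed the same day or within 30 days of the final intervention session".

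Two other places bear on the point. Objective 3.2.6 is "To examine how study results vary by cancer type", but section 7.2 treats cancer type as a separate exploratory subgroup and does not call it 'group'. Section 4.0 pays up to $100 "based on level of assessment completion", at $25 per assessment and $25 for the interview.

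**The concern.** A correlation between repeated measures can be estimated as a model parameter only if each person contributes at least two responses. With one baseline and one follow-up, moving baseline to the covariate side leaves one response. Keeping it on both sides makes the baseline row partly predict itself and distorts the residual correlation.

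The within-person correlation is one of the two quantities these models exist to supply. In a later trial with a baseline-adjusted comparison, the variance is proportional to 1 - ρ², which is 0.91, 0.75 and 0.51 for ρ of 0.3, 0.5 and 0.7. A planner who took a fitted zero at face value when ρ is really 0.7 would ask for about 1/0.51 = 1.96 times the sample needed.

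Because 'group', the covariance structure and the role of baseline are all left open, they would have to be settled at the analysis stage.

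**Working it through.** **Inputs.** One arm and n = 40 (sections 1.0 and 7.1); one baseline and one follow-up (sections 5.2 and 6.0). The plan attaches no figure to this model, so there is none to reproduce. It gives no correlation, so ρ = 0.3, 0.5 and 0.7 are assumed, with equal variance σ² at both times.

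**1. Baseline as covariate only.** There is one row per person, with residual variance σ_b² + σ_e² (between plus within). Only the sum enters the likelihood. In one simulated data set of 40, the REML log-likelihood was -131.2109 for intraclass correlations of 0, 0.25, 0.5, 0.75 and 0.99 alike. A standard mixed-model routine returned an arbitrary equal split (19.45 and 19.45) and warned that the Hessian was not positive definite. Time and 'group' have one level each, so a design with intercept, baseline, time and group has rank 2 of 4.

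**2. Baseline as both covariate and outcome row, with a time effect.** The slope on baseline is 1 in the baseline rows and ρ in the follow-up rows, so the pooled slope is (1+ρ)/2. In units of σ²:
- covariance of the two residuals: [(1-ρ)/2] × [ρ - (1+ρ)/2] = -(1-ρ)²/4
- residual variances: (1-ρ)²/4 and (1-ρ)(5+3ρ)/4, with mean (1-ρ)(3+ρ)/4
- compound-symmetry correlation: -(1-ρ)/(3+ρ)

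A random intercept cannot be negative, so it stops at zero. If the two residual variances are not pooled, the correlation is -√[(1-ρ)/(5+3ρ)] = -0.34, -0.28, -0.21. The size depends on the definition; the sign is wrong under both.

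**3. A third assessment, if there is one.** With equal correlations between all waves, the two follow-ups adjusted for baseline correlate at (ρ-ρ²)/(1-ρ²) = ρ/(1+ρ).

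**4. Both assessments as outcomes, no baseline covariate.** The correlation is a parameter of the model and is recovered.

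| Assumed ρ | Step 2, compound symmetry: theory (simulated) | Step 2, random intercept | Step 3: theory (simulated) | Step 4: simulated |
|---|---|---|---|---|
| 0.3 | -0.21 (-0.21) | 0.00 | 0.23 (0.24) | 0.31 |
| 0.5 | -0.14 (-0.15) | 0.00 | 0.33 (0.33) | 0.49 |
| 0.7 | -0.08 (-0.08) | 0.00 | 0.41 (0.40) | 0.70 |

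Simulated values are means over 200 multivariate normal data sets of 40 people for each ρ.

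**5. SD of change.** The raw SD of change is σ√[2(1-ρ)] = 1.18σ, 1.00σ, 0.77σ. The residual SD from regressing follow-up on baseline is σ√(1-ρ²) = 0.95σ, 0.87σ, 0.71σ. Their ratio is √[(1+ρ)/2] = 0.81, 0.87, 0.92. Neither is lost: the regression gives the adjusted SD, and the compound-symmetry fit in step 2 reproduced the raw SD of change. They are different quantities and need different labels.

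**6. Precision with 40 complete pairs.** By Fisher's z, atanh(0.5) ± 1.96/√37 gives a 95% CI of 0.22 to 0.70 for a correlation of 0.5. For an SD, √(39/χ²) gives limits of 0.82 and 1.28 times the estimate.

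**7. Number of assessments.** Two assessments plus the interview pay 2 × $25 + $25 = $75. The $100 ceiling implies ($100 - $25)/$25 = 3.

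**The case against.** The strongest reply is that nothing is lost from the data. With complete pairs, the ANCOVA slope times the ratio of the SDs equals the Pearson correlation exactly (0.627 both ways in a simulated check), so an analyst could recover it. That is true, and it places the fault in the specification. But the plan does not name that calculation; it names a mixed model whose own correlation parameter is unidentified or distorted.

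A second reply is that modelling a trajectory over time makes sense here only if baseline is among the responses, so the baseline adjustment may be loose wording for that. This is possible, but it conflicts with the word ANCOVA, and the text does not settle it. Step 2 likewise describes a reading the plan never spells out. It shows only that adding the baseline row while keeping the covariate does not rescue the model.

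Third, a second follow-up would make a correlation estimable. Step 3 shows that it would be the correlation conditional on baseline, which is a different target.

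Finally, these are additional analyses without hypothesis tests; section 7.2 makes SDs the main aim for these measures, and section 7.1 cites SDs in support of the sample size. This stands. No error rate is inflated and no treatment comparison is at risk, which limits the weight of the point.

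**Conclusion.** The concern holds. On the documented schedule, the model as worded returns either no within-person correlation or one that is zero or negative when the truth is positive. The exploratory subgroup and mechanism models have the same defect if they adjust for baseline. 'Group' has no meaning in one arm unless the plan supplies one; cancer type and clinic are both possible and neither is stated.

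Non-identifiability follows from having one response per person and needs no assumed value. The sizes under the other readings rest on the assumed correlations, equal variances and, for three waves, equal correlations. The consequence is confined to secondary estimates for planning later studies, so this should be fixed but does not threaten the study's main result.

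**What to change.** In section 7.2:

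- Define 'group' (for example as cancer type, if that is meant) or delete it.
- For the SDs and the correlation, specify a repeated-measures model with baseline and follow-up both as responses, a fixed effect of time, unstructured covariance, and no baseline value of the outcome as covariate. Report the SD at each time, the within-person correlation and the raw SD of change, each with a 95% CI.
- Report the residual SD from follow-up regressed on baseline separately, labelled as the baseline-adjusted SD of change.
- Use the same form in the exploratory models that target the within-person correlation. Other covariates may stay.
- State the number of patient-reported assessments and reconcile the payment in section 4.0 with sections 5.2 and 6.0. If there are three, extend the covariance to 3 × 3 unstructured.

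The cost is a change of wording in the analysis plan. The data and software stay the same.

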### **7.3 Accrual Rate**

The WFBCCC Survivorship Clinic has seen approximately 61 new cancer survivors (multiple cancer types) from July – December 2019 (approximately 10 per month). In addition, our team has experience recruiting and implementing a one-session self-management intervention with colorectal cancer survivors. We recruited 24 exclusively colorectal cancer survivors (36% of the 66 potentially eligible participants approached agreed to participate). Therefore, we conservatively expect to

## **SHARE-S Aim 3: Shared Healthcare Actions & Reflections Electronic systems in Survivorship**

Wake Forest Baptist Comprehensive Cancer Center (WFBCCC)  
WFBCCC # 99420

enroll 2-3 participants per month over 16 months to reach our accrual goal of 40.

### **7.4 Length of Study**

We estimate that we will complete study enrollment in 16 months, follow-up in 18 months, and analyses in 24 months.

## **8.0 Data Management**

Informed consent document	EPIC
E-referral documented, decline reasons	EPIC
Protocol Registration Form	WISER/OnCore
Demographic Factors	WISER/OnCore
Patient-reported Measures	REDCap
Intervention Fidelity Form	REDCap
Chart review: Clinical Factors	REDCap
Intervention Materials	Files on a local Secure Server in a folder accessible only by the study team
Process measures	Files on a local Secure Server in a folder accessible only by the study team
Patient adherence and text responses	Files on a Secure Server (tech system hosted at University of Massachusetts)
Qualitative feedback	Files on a local Secure Server in a folder accessible only by the study team
Adverse Events Log	WISER/OnCore

## **9.0 Confidentiality and Privacy**

Confidentiality will be protected by collecting only information needed to assess study outcomes, minimizing to the fullest extent possible the collection of any information that could directly identify subjects, and maintaining all study information in a secure manner. To help ensure subject privacy and confidentiality, only a unique study identifier will appear on the data collection form. Any collected patient identifying information corresponding to the unique study identifier will be maintained on a linkage file, stored separately from the data. The linkage file will be kept secure, with access limited to designated study personnel. Following data collection, subject identifying information will be destroyed consistent with data validation and study design, producing an anonymous analytical data set. Data access will be limited to study staff. Data and records will be kept locked and secured, with any computer data password protected. No reference to any individual participant will appear in reports, presentations, or publications that may arise from the study.

## **SHARE-S Aim 3: Shared Healthcare Actions & Reflections Electronic systems in Survivorship**

Wake Forest Baptist Comprehensive Cancer Center (WFBCCC)  
WFBCCC # 99420

Data collected in the eRefer portal (patient contact information) will be stored by the University of Massachusetts in a regulated environment until completion of the project or upon the request of the potential participant. The regulated environment provides applications to a secure network for collecting and storing confidential data. The regulated environment has been securely configured to allow application access via the secure socket layer (HTTPS) protocol. The regulated environment is secured using hardware and software firewalls, along with access restrictions to provide the needed security protocols for the regulatory and Federal standards required. Access is restricted through a Virtual Private Network, a secure RSA token, and only restricted personnel are allowed access to the regulated environment. The software program will use a secure Application Programmable Interface to send and receive the text messages. These text messages will be sent from toll-free number ([name]).

The texting service, also developed by the University of Massachusetts, will be responsible for sending the texts and receiving the text responses. The software program will use a secure Application Programmable Interface to the service to send and receive the texts. To minimize risks, text messages will not contain any personal health information. The software program will read the texting service servers to extract the data and enter the regulated environment. As soon as this is complete, the program will then delete the data from the texting service servers. The texting service does not store the phone numbers. It will only use the phone number to send and receive messages. During the informed consent process, participants will be informed of this potential risk to confidentiality through their sending and receiving text messages.

All data will be stored in a HIPAA compliant regulated environment and access will be only through a secure VPN network. All patient related identifiers are encrypted in the database. The regulated environment provides applications a secure network for collecting and storing confidential data. The regulated environment has been securely configured to allow application access via the secure socket layer (HTTPS) protocol. The regulated environment is secured using hardware and software firewalls, along with access restrictions to provide the needed security protocols for the regulatory and Federal standards required. Access is restricted through a Virtual Private Network, a secure RSA token, and only restricted personnel are allowed access to the regulated environment.

## **10.0 Data Safety and Monitoring**

The principal investigator will be responsible for the overall monitoring of the data and safety of study participants. The principal investigator will be assisted by other members of the study staff.

## SHARE-S Aim 3: Shared Healthcare Actions & Reflections Electronic systems in Survivorship

Wake Forest Baptist Comprehensive Cancer Center (WFBCCC)  
WFBCCC # 99420

### 11.0 Reporting of Unanticipated Problems, Adverse Events or Deviations

Any unanticipated problems, serious and unexpected adverse events, deviations or protocol changes will be promptly reported by the principal investigator or designated member of the research team to the IRB and sponsor or appropriate government agency if appropriate.

**SHARE-S Aim 3: Shared Healthcare Actions & Reflections Electronic systems in Survivorship**

Wake Forest Baptist Comprehensive Cancer Center (WFBCCC)  
WFBCCC # 99420

**Appendix A – Subject Eligibility Checklist**

IRB Protocol No. 000064683	WFBCCC 99420
Study Title: SHARE-S Aim 3: Shared Healthcare Actions & Reflections Electronic systems in Survivorship	
Principal Investigator: [name]	

Inclusion Criteria (as outlined in study protocol)	Criteria is met	Criteria is NOT met	Source Used to Confirm * (Please document dates and lab results)
Adults ≥18 years of age			
Documented or planned cancer survivorship visit			
Have a texting enabled telephone			
Cognitively able to complete study procedures as judged by the study team			
Able to understand, read and write English			
Exclusion Criteria (as outlined in study protocol)	Criteria NOT present	Criteria is present	Source Used to Confirm * (Please document dates and lab results)
Declined participation in the study			

This subject is  eligible /  ineligible for participation in this study.

ORIS Assigned PID: \_\_\_\_\_

Signature of research professional confirming eligibility: \_\_\_\_\_  
Date: \_\_\_\_\_

\* Examples of source documents include clinic note, pathology report, laboratory results, etc. When listing the source, specifically state which document in the medical record was used to assess eligibility. Also include the date on the document. Example: "Pathology report, 01/01/14" or "Clinic note, 01/01/14"

**SHARE-S Aim 3: Shared Healthcare Actions & Reflections Electronic systems in  
Survivorship**

Wake Forest Baptist Comprehensive Cancer Center (WFBCCC)  
WFBCCC # 99420

